### 10.4 Stopping Rules

Study contacts will be stopped if there is an acute and immediate concern for the safety of a parent or child. This would include the revelation of current abuse, neglect, suicidal or homicidal ideation. In addition, participants may choose to withdraw from the study at any point and for any reason.

## 11 Data Handling and Record Keeping

### 11.1 Confidentiality

All survey information will be collected from participants using a unique ID. Participants may complete surveys on paper, and the data will then be entered by research staff into a data base built with Research Electronic Data Capture (REDCap), a secure, HIPPA compliant web-based application hosted by BMC. Participants will have the option of entering data directly into the research database, which allows for direct electronic data capture under the participant's unique ID. The REDCap software allows researchers to design and implement study surveys for collecting, storing, retrieving, and manipulating data electronically. The data is stored in a secure database via an encrypted connection, and is immediately available to the investigator for analysis by a statistical package.

Downloaded data will reside on a secure, password protected server at Boston Medical Center (BMC) to which only designated individuals have access, thus providing a secure environment for all project data. Study data will be automatically backed up on a nightly basis. Files stored on BMC servers will be protected by electronic 'firewalls' that restrict access to designated users.

Any paper questionnaires (if participants prefer to complete it on paper in person) and source documents will be kept in study binders and stored in a locked cabinet, in a locked

office, in the BMC Psychiatry Research Center. Only the PI and psychiatry research staff will have access to this area. The “Master Code” linking subject IDs to identifiers will be password protected, only accessible to study staff, and will be located on a HIPAA-compliant, BMC controlled computer, in a folder on the secure BMC network that meets BMC standards for the storage of PHI. Survey data and qualitative interviews will be linked through the unique ID. Participant identifying information will not be collected for data analysis purposes.

The exit interviews will be audiotaped, with subjects’ permission, using a digital voice recorders or audio recording programs on our BMC encrypted study laptops. We will not be collecting any personal identifiable information from participants during the exit interview. If a participant accidentally mentions identifying information on the audio recording, this identifying information will be removed from the audio file and transcription. All participants will be reminded that they can decline to answer any questions if they so choose. Each digital audio file will be coded with subject unique identifiers, only connected to identifiers (PHI) via a separate, password-protected, master code. These files will be stored on a password-protected, encrypted BMC network. The coded audio file will additionally be sent to a BMC privacy office approved commercial service for transcription, or transcribed by a member of the research staff. For participants who are completely the intervention remotely through videoconference software (Zoom), their interviews will be audio recorded only. Once the interview is complete, the audio will be saved and coded with the subject unique identifiers, only connected to identifiers (PHI) via a separate, password-protected, master code.

All data for study purposes will be managed using the Boston University Medical Campus’ installation of REDCap data collection system, a software tool developed at Vanderbilt University and made available through the Clinical and Translational Science Awards network (CTSAs). To help protect and secure the data stored in REDCap’s database, the software application employs several methods to protect against malicious users who may attempt to identify and exploit any security vulnerabilities in the system. Access to the REDCap data entry website will be based on permissions granted by username and password which will be managed by the Boston University Clinical and Translational Sciences Institute for the Medical Campus Office of Information Technology (OIT). Only authorized study members will be able to enter or view data. The login information (username) of the person submitting the information, the date and time submitted, and other navigational information will be automatically obtained and stored in the database.

Boston University’s installation of REDCap is HIPAA compliant. Information posted on forms will be electronically encrypted using secure socket layering (SSL) encryption technology so that only the intended recipient can decode the data. Data will reside on a secure, password protected server at Boston University Medical Center (BUMC) to which only designated individuals have access, thus providing a secure environment for all project data. The database will be automatically backed up on a nightly basis. Files stored on BUMC servers will be protected by electronic ‘firewalls’ that restrict access to designated users. Restrictions and permissions to update the database will be controlled through the REDCap web application.

Because the server will be part of the BUMC network NT domain, only connections from users authenticated from the domain controller are accepted, thus providing a secure environment for all Center data. Specifically, the policy for computer systems security implemented at BUMC:

- Provide physical security of data. All central systems are physically secured behind locked doors with access restricted to key personnel in the OIT. Access through the primary door is also protected by an alarm system that is tied directly into the on-site central emergency response security control center. Written policies exist for contingencies to provide access to the room to those not explicitly authorized.
- Provide virtual security via connectivity. Internal access to all systems is done via Microsoft Challenge Handshake Authentication Protocol. With the exception of internet provider-based services, external client access must first gain access to the internal network before connecting to the systems. This connection is initiated via a Virtual Private Network connection using Point-to-Point Tunneling Protocol or through the University's modem pool which require Kerberos authentication.

All data are protected with disaster recovery via several methods:

- Hardware redundancy: Several stages of redundancy exist at the hardware level to minimize failure: dual-redundant power supplies exist on each disk array; hot-spare disk is configured to automatically self-heal in the event of a disk failure in the array; emergency power generators ensure a 100% electrical uptime; and uninterrupted power supplies present the systems with conditioned steady-state power.
- Data backup: The data are backed up on a regular schedule. All tapes are moved off-site on a daily basis and are stored in a fire-proof safe. Cycle-time of backups is approximately two months with the exception of a yearly archive which is retained for a one-year period.
- Data Security: All data are stored on NT File Systems with password-protected files and directories.

The BUMC REDCap Server has implemented a mix of preventive and detective security measures:

- Two factor authentication required for both admin and user access
- Require a password change every quarter for users
- Server is placed behind data center firewall
- Requires two-factor authentication and only permits for specific admin(s) that need to access the server
- Inform PIs that they need to remove investigators who are no longer involved, and periodically (ideally quarterly) review accounts
- Server is protected by intrusion prevention measures (firewalls/snort)
- Server is part of change management and vulnerability management programs to ensure server is patched within 30 days of vulnerability notification

Twilio is a third-party web service that provides the functionality for researchers to send REDCap survey invitations via SMS text messaging. When a BU REDCap admin enables Twilio for a REDCap project, BU REDCap verifies that the Twilio Request Inspector has been

disabled. This setting ensures that survey participants' phone numbers do not get permanently logged on Twilio's servers, but instead remain securely in the BU encrypted REDCap server.

If the study staff learns of any acute safety concerns, such as current thoughts about suicide, self-harm, or intent to harm others, abuse, neglect, or other reportable conditions, investigators may need to break confidentiality to prevent this harm from happening. Participants are made aware of this during the consenting process. Study staff will abort study procedures and take the necessary steps to keep the participant and child from harm. The study Principal Investigator will be immediately notified by pager. Children or parents may be referred for emergency evaluation at the Boston Medical Center Psychiatric Emergency Services or at the Boston Emergency Services Team (BEST) located near the hospital. We also may contact treating health care providers to be sure they are aware of the risk identified. In addition, if research staff identify any concern for current abuse or neglect, they will page the study investigator who must report this to the Department of Children and Families.

## 11.2 Source Documents

This study will utilize REDCap (Research Electronic Data Capture), a software toolset and workflow methodology for electronic collection and management of clinical and research data, to collect and store survey data. REDCap will be utilized to collect and store data obtained through surveys and assessments. The Boston University School of Medicine Research Department will be used as a central location for data processing and management. REDCap provides a secure, web-based application that provides an intuitive data manipulation interface, custom reporting capabilities, audit trail functionality, real-time data monitoring/querying of participant records, and variations of data exporting/importing. Paper questionnaires and source documents will be kept in study binders and stored in a locked cabinet, in a locked office, in the BMC Psychiatry Research Center. Only the PI and psychiatry research staff will have access to this area.

The exit interviews will be audio recorded on a digital voice recorder or through an audio recording programs on our BMC encrypted study laptops, and the audio recordings will be transcribed by a commercial transcription service. The interviewer may also take notes throughout the intervention and exit interview and these notes may also serve as source documents for study data. The recordings, transcriptions, and notes will be stored in a locked file cabinet. Electronic versions of the transcriptions will be password protected and stored on a secure network. The transcriptions and notes will be retained for at least seven years after the completion of the study and will be destroyed after the publication of the final journal article that uses this data. The audio files will be destroyed after they have all been transcribed.

## 11.3 Study Records Retention

Survey data and study notes will be retained for at least seven years after the completion of the study and will be destroyed after the publication of the final journal article that uses this data.

## 12 Statistical Plan

### 12.1 Study Hypotheses

Our hypothesis is that reducing unmet social needs will lead to improved ADHD symptoms via multiple mechanisms, including: 1) reduced child and parent stress; 2) increased parent empowerment and activation, and 3) improved connection to needed mental health care.

### 12.2 Sample Size Determination

Based on [name] mentorship team's past experience optimizing interventions, we believe that intervention testing and iterative improvement with 30 intervention participants will be adequate to create an optimized intervention ready for study in a fully powered RCT. We will not estimate effect size, since this can be misleading in a pilot study. To power a future RCT we will obtain within-group standard deviation of continuous outcome measures and correlation over time of outcome measures at baseline and follow up. Since group means on continuous variables typically begin to stabilize around 15 participants per group, the proposed sample size of 30 participants per group, even after 25% attrition, will allow us to evaluate the potential of the intervention while remaining within the budgetary parameters.

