## 5 Study Design

This study is a pilot randomized control trial. Participants are parents of preschool aged children between the ages of 3-5 years old with either an ADHD diagnosis OR with a score  $\geq$  80th percentile on the Preschool Version of the ADHD Rating Scale-IV. Potentially eligible participants will be referred to the study team by pediatric providers via the electronic medical record (EMR), or identified via EMR screening. Following eligibility screening, informed consent, and completion of baseline questionnaires, participants will be randomly assigned to treatment methods of either the interventional treatment (PRE-CARE) or control treatment (care as usual). All participants will be sent baseline and follow-up questionnaires to complete either electronically via REDCap, in-person with an RA using pencil/paper, or verbally with an RA (depending on participant preference). Participants randomized to PRE-CARE will also complete feasibility and acceptability measures including an exit interview.

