### Parent-Reported Study Assessments

In addition to the baseline assessments, all 60 participants (30 intervention and 30 control) will complete follow-up assessments at 3, 6, and 12 months following the completion of baseline assessments. Follow-up assessments can be completed in person at the research office, in the participant's home, or remotely by phone or videoconference.

Participants in the intervention arm only will also be invited to participate in an in-depth exit interview once their intervention period is complete in order to collect feedback on the intervention content and strategy and explore putative intervention mechanisms. If participants refuse to participate in the exit interview, but complete the survey assessments, they will still be compensated.

At any of the assessment timepoints, if participants refuse to complete select questions in the assessments, but answer most questions, they will still be compensated.

It is anticipated that in some cases, two primary caregivers will desire to be part of the intervention. Other adult family members involved in primary caregiving may also participate in any intervention sessions as long as the consenting primary caregiver is present for all sessions and is the only one completing all intervention assessments.

At baseline, participants will complete a Contact Information form that details their preferred mode of contact for completion of follow-up assessment (email, phone, mail). At each subsequent time point, RAs will refer to the contact information form and send reminders (via email, phone, or text message, based on preference) to the participant to complete their follow-up assessments every 4 days for at least 2 weeks (or until the assessment is complete). RAs will run weekly reports off REDCap to see which participants have not completed their assessments. If a participant has not completed their assessment after 2 weeks, the RA will call the participant to complete the assessment over the phone. At each of the follow-up timepoints (3, 6, and 12-months after baseline), RAs should stop reminder calls to participants 8 weeks after the participant was initially contacted to complete the assessment.

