### 12.3 Statistical Methods

Because this is a pilot study, it is not fully powered to detect differences between groups. Because of emerging consensus that group-to-group comparisons in a pilot study are invalid and misleading, estimating effect size is not one of our study objectives. However, our goal will be to obtain estimates of study parameters to inform power calculations for a subsequent study, including the following:

- Within-group standard deviation of each continuous primary and secondary outcome measure as well as each measure of target engagement; and
- Correlation over time of each outcome measured at baseline and follow-up.

Furthermore, our collection and analysis of process measures will be used to inform changes to the intervention throughout the pilot study in order to optimize its delivery for a future RCT.

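### Does resting 30 per group on the stability of means undermine a pilot that is meant to supply SDs and correlations?

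*Combined protocol and SAP*

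**What the plan says.** Section 12.2 supports the sample size in three ways. The mentorship team's experience is that 30 intervention participants are enough to optimize the intervention. On the statistical side it says "Since group means on continuous variables typically begin to stabilize around 15 participants per group", so that 30 per group, after 25% attrition, "will allow us to evaluate the potential of the intervention". The size also fits the budget.

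The same section names what will be carried forward: "To power a future RCT we will obtain within-group standard deviation of continuous outcome measures and correlation over time of outcome measures". Section 12.3 states that "estimating effect size is not one of our study objectives" and lists two kinds of parameter: "Within-group standard deviation of each continuous primary and secondary outcome measure", extended to the measures of target engagement, and "Correlation over time of each outcome measured at baseline and follow-up". Section 9 (Parent-Reported Study Assessments) has all participants "complete follow-up assessments at 3, 6, and 12 months following the completion of baseline assessments".

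Neither 12.2 nor 12.3 states the expected precision of an SD or a correlation, whether each is shown by arm or pooled within arms, or whether confidence limits accompany it.

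**The concern.** The one statistical argument concerns means, while neither parameter named for planning the next trial is a mean. The standard error of a mean says nothing direct about the error of an SD or a correlation. A reader of 12.2 might conclude that 30 per group makes the planning inputs firm, when an SD from a sample this small remains fairly uncertain and the next trial's sample size depends on its square.

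The reporting also looks open. A within-group SD could come from each arm or be pooled within arms, and with three follow-up visits there are up to three baseline-to-follow-up correlations per measure. If the choice were made after seeing the data, a convenient value could be carried into the next power calculation. At stake is the sample size of a later trial; nothing in this one depends on it.

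**Working it through.** **Inputs.** 30 per arm and 25% attrition (12.2); follow-up at 3, 6 and 12 months (section 9). The documents give no alpha, power, effect size, SD or correlation, so r = 0.3, 0.5 and 0.7 are assumed.

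**The plan's own arithmetic.** 30 × 0.75 = 22.5 per arm, above the benchmark of 15. Reaching 15 completers would need 15 / 0.75 = 20 per arm. So 30 exceeds the benchmark and is not derived from it. Nothing here is inconsistent. Below, 22 per arm (44 in all) is used.

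**Is the statement about means reasonable?** The SE of a mean, in SD units, is 1/√n:

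| n | 5 | 10 | 15 | 22 | 30 |
|---|---|---|---|---|---|
| SE | 0.45 | 0.32 | 0.26 | 0.21 | 0.18 |

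From 5 to 15 the SE falls by 0.19; from 15 to 30 it falls by 0.08. There is no threshold, but returns diminish, which is a fair reading of means that begin to stabilize.

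**Precision of an SD.** The 95% limits, as multiples of the estimate, are √(df/χ²), with χ² at its 97.5% and 2.5% points. The variance multiple is df/χ². It carries over to the next trial's N if the target difference is fixed in raw units and there is no baseline adjustment.

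| Basis | df | χ² points | SD multiple | Variance (N) multiple |
|---|---|---|---|---|
| One arm of 22 | 21 | 35.48, 10.28 | 0.77–1.43 | 0.59–2.04 |
| Pooled within arms, 44 | 42 | 61.78, 26.00 | 0.82–1.27 | 0.68–1.62 |
| Pooled within arms, 60 | 58 | 80.94, 38.84 | 0.85–1.22 | 0.72–1.49 |

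Taking 45 completers (df 43) gives 0.83–1.27, so rounding 22.5 down to 22 is immaterial. Even with no attrition the N multiple spans 0.72–1.49, so much of the uncertainty comes with any pilot of this size.

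**Precision of a correlation.** Fisher z with SE = 1/√(22 − 3) = 0.229 for one arm, and 1/√(19 + 19) = 0.162 when the two arms' z values are combined.

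| Assumed r | One arm of 22 | Pooled within arms | N multiple, pooled |
|---|---|---|---|
| 0.3 | −0.14 to 0.64 | −0.01 to 0.56 | 0.76–1.10 |
| 0.5 | 0.10 to 0.76 | 0.23 to 0.70 | 0.68–1.26 |
| 0.7 | 0.39 to 0.87 | 0.50 to 0.83 | 0.61–1.47 |

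The last column is (1 − limit²)/(1 − r²), with a negative limit set to 0. It applies only if the next trial adjusts for baseline, and it takes the SD as known.

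**Does the text leave the analyst stuck?** Both parameter types are named, within-group rules out an SD that mixes in a difference between arms, and the follow-up visits are defined in section 9. The Schedule of Events in the Appendix shows which measures are taken when. Feasibility measures exist in one arm only (section 5: "Participants randomized to PRE-CARE will also complete feasibility and acceptability measures including an exit interview"), so for them pooling does not arise. What remains is to attach n and limits and to label the arm and visit, which is ordinary practice.

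**The case for a change.** The best case for a change is that it costs two or three sentences and serves a stated purpose: section 3.2 includes obtaining parameters to plan a properly powered trial, and section 4.1 says a future study will be powered from them. Fixing the reporting in advance would stop anyone choosing between a one-arm SD and a pooled SD after the fact, and the two differ in what they imply (upper N multiple 2.04 against 1.62).

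That much stands: 12.2 is silent on precision, and a sentence would do no harm. Three things weaken it.

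- SDs and correlations are not the whole output of the pilot. Section 4.1 puts logistics, delivery and mechanisms as the main objectives, and the list in 12.3 is introduced as a partial one. Section 12.2 ties the sentence about means to judging the intervention's potential, which can be done by describing each arm without an effect size.
- Writing bare limits into the protocol could mislead. Chi-square limits for an SD are sensitive to skewness. Simulating two arms of 22 with gamma data (skewness assumed, as the documents give none), nominal 95% limits covered about 88% of the time at skewness 1, 81% at 1.4 and 71% at 2. Scales such as the PHQ-9 or ACE-Q could be skewed.
- Any reader can form the same limits from the published SD or correlation and its n, so prior wording adds little information.

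**Conclusion.** No change is needed. The observation is accurate: an argument about means does not describe the precision of SDs or correlations. But this is missing detail that an analyst fills sensibly, and nothing in the plan is in error. Section 12.2 also rests the size on optimization experience and budget, nothing shows 30 per group to be wrong, and a pilot that disclaims power to compare groups has no need of a power calculation.

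At 22 completers per arm, a pooled SD is known to within about 0.82 to 1.27 times its estimate (0.68 to 1.62 on the scale of an unadjusted N), and a correlation assumed to be 0.5 to within 0.23 to 0.70. These figures assume approximate normality, independent families, and similar SDs and correlations in the two arms. They show how cautiously the next trial's planners should treat the inputs; they do not alter who is enrolled, what is measured or what this pilot will report.
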